For this menthol / nicotine reinforcement study, the Test Sessions will be conducted after an Adaptation Session is completed where subjects will learn to use the e-cigarette for delivering the menthol or control (tobacco) flavor. A short e-cigarette questionnaire will also be administered during the Adaptation Session. Then, the nicotine Test Sessions will be performed following overnight abstinence from tobacco. Smokers will be assigned a random sequence of three different e-cigarette conditions (low menthol (0.5% or 5 mg/mL) plus tobacco flavor, high dose menthol (3.5% or 35 mg/mL) plus tobacco flavor or tobacco flavor alone for each of the three Test Sessions (a different menthol condition for each session). The concentration of tobacco flavor will be identical across all conditions. The amount of menthol in high dose condition is the same as those found in commercially available mentholated e-cigarette solutions (AmericaneLiquidStore™). The low dose menthol solution contains menthol that is minimally perceptible by smokers and is in the range of e-cigarette solutions targeting smokers with a preference for low menthol impact in the e-cigarette vapor. In each Test Session, smokers will receive a random order of one intravenous delivery of saline, and two intravenous deliveries of nicotine (3.6 mcg/kg and 7 mcg/kg or 0.25 mg/70 kg and 0.5 mg/70kg), just after the menthol or control flavor is delivered via the e-cigarette. The intravenous dose deliveries will be one hour apart to provide sufficient time for the nicotine and menthol effects to wear off. The nicotine infusion sessions will be at least 24 hours apart to minimize carryover nicotine effects. The main outcome measure will be subjective drug effects as measured with the Drug Effects Questionnaire (DEQ). Other outcomes include cardiovascular measures, cognitive performance, and self-report measures of nicotine withdrawal. Cardiovascular measures include heart rate, systolic and diastolic blood pressure. Cognitive performance will be assessed with the Stroop test, mathematical processing test (MPT), and continuous performance test (CPT). Nicotine withdrawal measures will be measured with the Nicotine Withdrawal Symptom Checklist (NWSC) and the Brief Questionnaire on Smoking Urges (BQSU).

B. Dose Finding Study

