- b) Test Sessions: Experimental sessions will start around 8:30 AM. As summarized in Table 2, baseline biochemical measures will include urine menthol glucuronide and cotinine, plasma nicotine, and for women, estradiol and progesterone levels. These samples will be obtained followed by cognitive testing. Subjects will then start inhaling from the e-cigarette with the assigned menthol condition (control flavor, low or high dose of menthol), one inhalation every 15 seconds as practiced in the adaptation session. It will take approximately 90 seconds to complete 6 inhalations. Subjects will then receive the first delivery of the assigned injection (saline, 0.25 mg/70 kg or 0.5 mg/70 kg nicotine). Each study injection will be 60 minutes apart to provide sufficient time for the physiological and subjective nicotine effects to return to baseline. Following each injection, physiological, subjective, and cognitive outcome measures will be obtained.
- c) Medical monitoring: For nicotine test sessions, a physician will be present and subjects will be attached to a blood pressure and heart rate monitoring device. An IV catheter will be in place throughout the session. Subjects will be administered nicotine only if the systolic blood pressure is <150 mmHg and heart rate is <100 beats/minute. Subjects will be terminated from the study if the blood pressure at any time is >170/110 mm Hg, the heart rate is >120 beats/min, or if they develop signs and symptoms compatible with nicotine toxicity. Subjects

[Type text]

[Type text]

will remain in the laboratory for three hours after the last nicotine administration. These procedures have been developed as part of our IND application for IV nicotine.

Table 2. Schedule of Events: Experimental Session*

Time	Measures and Events
8:00 AM	(Building 36) CO level, urine sample, BAL, and light standard breakfast
9:00 AM	(Biostudies Unit) blood sample. HR/BP, EKG, M-NWSC, BQSU, SAFTEE, Cognitive Testing
11:00 AM	Menthol (control, high or low Menthol) DEQ + IV Saline or Nicotine (0.25 or 0.5mg/70 kg) blood draw
11:01	HR/BP, DEQ
11:02	HR/BP
11:03	HR/BP, DEQ,
11:05	HR/BP, DEQ
11:08	HR/BP, DEQ blood draw
11:10	HR/BP, DEQ
11:15	HR/BP, DEQ, Cognitive Testing
11:30	HR/BP, DEQ blood draw
11:45	HR/BP, DEQ
11:55	HR/BP, DEQ, BQSU
12:00	Menthol (control, high or low Menthol) DEQ + IV Saline or Nicotine (0.25 or 0.5 mg/70 kg), blood draw
13:00	Menthol (control, high or low Menthol) DEQ + IV Saline or Nicotine (0.25 or 0.5 mg/70 kg), blood draw

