The main outcome measures will be the “good effects” and “drug liking” items of the DEQ. Mixed effects models will include the within-subject factors nicotine dose (0.25, 0.5 mg nicotine or placebo), menthol dose (low dose of menthol, high dose of menthol, or control flavor) and time of measurement (+1,+3,+5,+10,+15,+30,+45,+55 minutes); the between-subject factor types of cigarette preference (menthol vs. non-menthol) and all possible interactions among these factors. We will also consider order effects for nicotine dose (1, 2 or 3) and session day (1, 2 or 3) and the effects of potential covariates (race, sex, baseline plasma NMR, FTND scores). These effects will be included in the final model if significant. Estradiol and progesterone levels will also be considered as potential covariates in a secondary analysis of women only. We will consider several different correlation structures for the repeated measures within individuals, and will select the best fitting one based on Schwartz Bayesian information criterion. SAS PROC MIXED will be used for the mixed-model analyses.

A significant interaction between nicotine dose and menthol dose, with significantly higher response to menthol + nicotine compared to control flavor + nicotine or control flavor + saline will be considered supportive of hypothesis 1A. A significant interaction between nicotine dose, menthol dose, and group (menthol vs. non-menthol smokers), with significantly stronger effects in menthol smokers than in non-menthol smokers, will be considered supportive of hypothesis 1B. We expect significant effects for both doses and will also test for dose-dependent effects.

[Type text]

[Type text]

Rationale for sample size: Both studies have 80% power to detect large effect sizes ($f=0.4$) for the interactions of interest in repeated measures analysis with 30 subjects per group for a total of 60 subjects at 0.05 significance level. Our preliminary data for both outcome measures show larger magnitude effects for the nicotine effects (all $f>0.5$) and menthol effects are expected to be similarly strong (Sofuoglu et al. 2009a). Applying Bonferroni correction and using an alpha level of 0.01 we have 80% power to detect post-hoc comparisons of medium to large effect size $d'=0.7$ for the menthol and nicotine effects. Our previous study shows larger effects of nicotine $d'>1.0$. To account for up to 70% dropout we will recruit 160 subjects for a target of 60 completers.

13. Risks and benefits

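### The DEQ rating listed just before each infusion is left out of the model; entering it, centred within session, could sharpen the interaction tests at little cost

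*Protocol*

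**What the plan says.** Table 2 (Schedule of Events: Experimental Session) gives the 11:00 step as "Menthol (control, high or low Menthol) DEQ + IV Saline or Nicotine (0.25 or 0.5mg/70 kg) blood draw", with equivalent entries at 12:00 and 13:00. Read in listing order, a DEQ is completed after vaping and before the infusion, three times per session. The prose in Study Procedures, b) Test Sessions, goes from the inhalations to the injection without mentioning it.

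Section 12 makes the good-effects and liking items of the DEQ the main outcomes and sets "time of measurement (+1,+3,+5,+10,+15,+30,+45,+55 minutes" as the time factor. The candidate covariates are "the effects of potential covariates (race, sex, baseline plasma NMR, FTND scores", plus hormone levels in a women-only analysis. Sequence enters as "We will also consider order effects for nicotine dose (1, 2 or 3", with session day treated the same way; these terms and the covariates stay in the model only if significant.

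On allocation, section 11.A says: "In each Test Session, smokers will receive a random order of one intravenous delivery of saline, and two intravenous deliveries of nicotine". Menthol is fixed for the whole session ("a different menthol condition for each session"). For washout, the protocol relies on spacing: "Each study injection will be 60 minutes apart to provide sufficient time".

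**The concern.** A rating of the outcome items taken immediately before each infusion is the natural baseline for that infusion, yet it is neither an outcome time nor a covariate. Every named covariate is a subject-level measure or an order term. None describes the subject's state just before a given infusion.

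The position term does not fill the gap. Saline in position 2 may follow either nicotine dose, and position treats the two cases alike. Because each dose is given once per session, a dose never follows itself. Any residue therefore falls unevenly on the doses and pulls the nicotine-minus-saline difference towards zero.

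What is at stake is precision, and possibly a small attenuation, in the interaction tests that section 12 requires for hypotheses 1A and 1B.

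**Working it through.** **The plan's own figure.** Section 12 states 80% power for the interactions at f = 0.4 with 60 subjects. With λ = N·f² = 60 × 0.16 = 9.6, a two-group F test gives 86%, 2 df gives 78% and 4 df gives 65–69%. Repeated-measures within-between formulas give over 99% at every correlation tried (0 to 0.7). None returns 80%, and the protocol states neither the degrees of freedom nor the correlation. Below, 80% serves only as a starting point.

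**Step 1: does adjustment distort the interaction?** The current nicotine dose cannot affect a rating made before it. With random dose order and no carryover, the pre-infusion rating has the same expectation at each dose within a session. Adjustment with a common slope therefore leaves nicotine minus saline unchanged in expectation in every session, and so leaves its difference between menthol conditions unchanged. A simulation of the 3 × 3 design (60 subjects, 4,000 runs, within-session analysis with position terms, assumed variances, r = 0.5) with a true interaction of 0.75 gave 0.753 unadjusted and 0.751 adjusted. With no true interaction, the adjusted test rejected in 5.1% of runs. A generalised-least-squares variant of the adjusted analysis rejected in 7.4%. It had no unadjusted counterpart, so that excess cannot be attributed to the covariate; the 5% result belongs to the within-session analysis.

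**Step 2: power.** Let r be the within-session correlation of pre- and post-infusion ratings (an assumption; not in the protocol). Residual variance is multiplied by 1 − r², so

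power = Φ[(1.960 + 0.842)/√(1 − r²) − 1.960].

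| r | √(1 − r²) | power |
|---|---|---|
| 0 | 1 | 80.0% |
| 0.1 | 0.995 | 80.4% |
| 0.3 | 0.954 | 83.6% |
| 0.5 | 0.866 | 89.9% |
| 0.7 | 0.714 | 97.5% |

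In the simulation, power was 83% with and without adjustment at r = 0, and rose from 83% to 91% at r = 0.5. A second 3 × 3 simulation with other assumed variances also showed no change at r = 0, and a rise from about 66% to 75% at r = 0.45.

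**Step 3: carryover.** Let saline, low and high have effects 0, L and H, and let a fraction c of the preceding effect persist into the post-infusion ratings. Each dose comes first with probability 1/3; otherwise it follows one of the other two with equal probability. The expected residue is cL/3 on the high dose and c(L + H)/3 on saline. Hence

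high − saline = H + cL/3 − c(L + H)/3 = H(1 − c/3).

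The low dose has the same factor, and so does the interaction. Now let cB and cY be the fractions left in the pre- and post-infusion ratings, and b the covariate slope. The adjusted factor is 1 − (cY − b·cB)/3.

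| cB | cY | unadjusted | b = 0.3 | b = 0.5 | b = 1 |
|---|---|---|---|---|---|
| 0.25 | 0.25 | 0.917 | 0.942 | 0.958 | 1.000 |
| 0.25 | 0 | 1.000 | 1.025 | 1.042 | 1.083 |

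Correction is complete only when b = cY/cB. In simulation with 25% carryover in both ratings and r = 0.5, the estimate moved from 0.686 to 0.719 of 0.75. The shortfall fell from 0.064 to 0.031, about half, and power rose from 75% to 90%. With 15% carryover and a true interaction of 8 mm, the formula gives 8 × (1 − 0.05) = 7.6; the second simulation gave 7.65 unadjusted and 7.81 adjusted. With no true interaction, carryover created none (0.001 either way).

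**Step 4: the simple menthol comparisons.** The rule for 1A also compares menthol plus nicotine with control flavor plus nicotine. If the rating follows vaping, it carries part of menthol's effect. The raw covariate lowered this contrast from 1.35 to about 0.99 in the first simulation, and from 16.1 to 12.5 in the second. The session-centred rating sums to zero within a session and so cannot absorb anything constant within it: the contrast stayed at 16.1, with the same interaction gain.

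**The case against.** The strongest reply is that nothing here is wrong. An unadjusted within-subject interaction test is valid, the protocol speaks only of potential covariates, and the statistical analysis plan may settle baseline handling. That stands as far as validity goes. But section 12 itself lists the factors, times, candidate covariates and retention rule, and this rating appears in none of them, so naming it is a concrete change.

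Three further points stand:

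- No passage reports a residue at 60 minutes, and the DEQ is followed to +55 minutes, so a residue would be visible. The carryover fractions above are assumptions.
- Subject and session differences already cancel in the interaction, and a rating made before any drug may track later liking only weakly. The gain could be close to nil.
- The rating's timing rests on the order of items in a table cell, and the three-way test for 1B was not simulated. Step 1 carries over to it; the size of the power gain is inferred.

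A reader might infer that adjustment eliminates carryover, or that it always adds power. The protocol supports neither: the first needs b = cY/cB, and the second needs a correlation that it does not give. With carryover, the rating is also associated with the current dose, so unbiasedness is conditional.

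The objection that one decision rule would then span two models is met by centring within session.

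**Conclusion.** The point holds as a cheap improvement. The planned test is valid, and a reader who infers that it is biased or invalid for lack of this covariate goes further than the documents allow. Adjusting the interaction tests keeps type I error near 5% in the within-session analysis and is unbiased given no carryover and a common slope across doses. From an 80% base the gain runs from nothing at r = 0, through about 4 points at r = 0.3, to about 10 at r = 0.5. Carryover costs at most c/3 of the effect, for example 5% when c = 0.15. Adjustment recovers part of that, and can overshoot slightly (4.2% in the case shown with b = 0.5) if the residue has gone by the post-infusion ratings.

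**What to change.** Before unblinding, pre-specify in section 12 that each outcome item's pre-infusion score, minus its mean over the infusions of that session, enters the primary model as an infusion-level covariate whether or not it is significant. The alternative is to use the raw score for the two interaction tests only and leave the simple menthol comparisons unadjusted, at the price of two models. State in Study Procedures that this DEQ is completed after vaping and before the infusion, if that is what is meant. A preceding-dose term in a sensitivity analysis would check carryover directly.

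The cost is one more model term. No new data are needed if the rating is collected as Table 2 lists it. The downside is a gain that may be small.

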Menthol is a flavoring agent that is used in a wide range of products. It has also commonly been used as an additive in cigarettes since the 1920s. Menthol has a well-described cooling and soothing action in the airways that may reduce the harshness of tobacco smoke. These effects make menthol cigarettes particularly appealing among youth who are experimenting with cigarettes. In fact, among 12 to 17 year-olds, 44.7% smoke menthol cigarettes, compared to 30.1% of adults aged 26 or older (Rock *et al*, 2010). Among young smokers, menthol cigarette use is especially common in African-Americans (71.9%), compared to Hispanic (47%) or Non-Hispanic Caucasians (41%) (Rock *et al*, 2010). In several cross-sectional studies, menthol cigarette smoking has been found to be a risk factor for development of dependence (Collins and Moolchan, 2006; Hersey *et al*, 2006; Muscat *et al*, 2009; Wackowski and Delnevo, 2007). More recently in a prospective study in smokers 17 or younger, initiation of smoking with menthol cigarettes was associated with higher risk of progression to established smoking and higher levels of nicotine dependence (Nonnemaker *et al*, 2012). A recent report by the Tobacco Product Scientific Advisory Committee (TPSAC) concluded that there was evidence to support the relationship between menthol cigarettes and smoking uptake, especially in African-Americans (Benowitz and Samet, 2011). Collectively, these studies demonstrate an association of menthol cigarettes with smoking initiation, higher levels of dependence, and difficulty in quitting smoking. Thus, there is a clear need for further research on the role of menthol in multiple aspects of nicotine dependence in order to provide guidance for developing policies regarding menthol.

c) Menthol's Biological Effects - Published Studies

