We are proposing a double-blind, placebo-controlled study that enrolls young adult smokers stratified for menthol preference. Menthol and control flavor will be delivered via an e-cigarette just prior to saline or IV nicotine infusion. This menthol / nicotine reinforcement study was preceded by a separate menthol dose-finding study that determined the low and high doses of menthol to be administered by the e-

[Type text]

[Type text]

cigarette. For this dose-finding study, subjects were screened at the West Haven site where the IV nicotine study will be performed, but the dose-finding study was conducted at the John Pierce Labs located on the Yale Campus located about 2 miles from the West Haven site. The screening procedure for the dose-finding study was described in a separate screening consent form. The dose-finding study did not administer any nicotine.

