Determination of the menthol doses: Once a subject completed the testing, a grand log-means of the intensity ratings were used to determine the menthol test concentration that best matched the overall intensity of the popular commercial product. This was determined to be the high dose of menthol. The low dose was determined as the menthol concentration at which subjects could discriminate effects vs. the no menthol control condition, but at which clear differences in ratings were observed as compared to a

[Type text]

[Type text]

clustering of responses (response plateau) at higher menthol concentrations. In addition to these studies, [name] laboratory analyzed the concentrations of menthol in the commercially available mentholated e-cigarette solution (about 35 mg/cc). Based on these findings, we chose two menthol doses that will be used in our study. While the high dose will have the same concentrations of menthol in mentholated e-cigarette solution (AmericaneLiquidStoreTM), the low dose will be minimally recognizable by participants as menthol flavor (about 5 mg/cc).

Potential additional learning from sensory testing: In addition to establishing menthol concentrations for clinical testing, the psychophysical data will also enable preliminary evaluation of potential sex and/or race differences in sensory and hedonic responses to menthol. The discovery of such differences would yield novel data on how inhaled menthol is perceived differently between these groups, and how these differences might contribute to variations in the enhancing effects of menthol on nicotine reinforcement.

C. Medical Monitoring and Safety

Subjects will be given a thorough physical examination prior to entry in the study. A physician will be present at all test sessions. Subjects will be attached to blood pressure and heart rate monitoring devices throughout each test session. An IV catheter will be in place throughout the session. Subjects will be administered nicotine only if the systolic blood pressure is <150 mmHg and heart rate <100 beats/minute. The subject's participation will be terminated if their blood pressure at any time is >170/110 mm Hg, the heart rate is >120 beats/min, or if the subjects develop signs and symptoms compatible with nicotine toxicity. Subjects will be monitored for two hours after the last nicotine administration.

D. Measures

a) Physiological:

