- Heart rate and blood pressure: Heart rate and blood pressure readings will be taken at screening, and during each test session to measure nicotine's effect on these parameters

b) Biochemical:

- Serum estradiol and progesterone analysis (females only): Serum estradiol and progesterone levels will be measured before each test session, and will be used as covariates in our analysis, since female sex hormones may contribute to sex differences in nicotine responses (Lynch *et al*, 2010).
- Plasma cotinine and 3-hydroxycotinine (3HC): Plasma cotinine and 3-hydroxycotinine levels will be measured from blood obtained during the three Test Sessions to determine the nicotine metabolite ratio (NMR). The NMR is the ratio of 3HC, the main metabolite of cotinine, to cotinine and reflects the activity of cytochrome P450 (CYP) 2A6 and thus, the rate of nicotine clearance (Dempsey *et al*, 2004). NMR has been shown to be stable in smokers during ad-lib and reduced smoking (Mooney *et al*, 2008). Plasma samples for 3HC will be obtained at baseline, and the NMR will be included as a covariate in our analyses.

[Type text]

[Type text]

Plasma nicotine: Plasma nicotine levels will be measured from blood that was obtained prior to the first experimental vaping session on each test day to characterize the subject's smoking status.

- Urinary cotinine levels: A semi-quantitative rapid urine level of cotinine will be obtained at screening to confirm smoking status at study entry.
- Urine menthol glucuronide levels: Urine samples will be obtained at intake to confirm the menthol preference of smokers (Benowitz *et al*, 2010). Additional urine samples will be collected throughout each test session to measure the amount of menthol exposure (via urinary menthol glucuronide levels) that was provided by the e-cigarette.
- Plasma menthol glucuronide levels: Blood samples will be obtained throughout each test session to determine the amount of menthol delivered by the e-cigarette. Blood samples will be obtained prior to each of the three experimental vaping sessions, and at 2 time points after each nicotine or saline infusion. An additional blood sample will be obtained just prior to removing the IV. Plasma levels of menthol glucuronide will be measured at different time points to generate concentration-time curves for each menthol delivery. This will help characterize the pharmacokinetics of menthol and account for differing menthol exposure between subjects.

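### Order terms and covariates enter the main-outcome model only if significant, which conflicts with the unconditional statement that the nicotine metabolite ratio is a covariate

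*Protocol*

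**What the plan says.** Section 12 (Data analysis methods) fixes the tested part of the model: nicotine dose, menthol dose, time, cigarette preference and all their interactions. It then names further terms that will only be considered: infusion order (1 to 3), session day (1 to 3), race, sex, baseline plasma NMR and FTND score. Their entry rule is: "These effects will be included in the final model if significant". No level is given for this screen, and the text does not say whether one final model serves both main outcomes.

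Section 11.D b (Biochemical measures) speaks differently about NMR: "the NMR will be included as a covariate in our analyses".

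For estradiol and progesterone, in a bullet limited to females, section 11.D b says that "levels will be measured before each test session, and will be used as covariates in our analysis". Section 12 says: "Estradiol and progesterone levels will also be considered as potential covariates in a secondary analysis of women only".

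Hypothesis 1A needs a significant nicotine × menthol interaction together with a higher response to menthol plus nicotine than to the control-flavor conditions. Hypothesis 1B needs a nicotine × menthol × preference interaction, "with significantly stronger effects in menthol smokers than in non-menthol smokers, will be considered supportive of hypothesis 1B".

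**The concern.** Choosing adjustment terms by their own p-values means that the model for the main outcomes is not known until the data have been seen. Good effects and drug liking could end up adjusted for different things, although they serve the same hypotheses. The order terms belong to the design of a crossover with randomised orders, so there is little reason to make them earn their place.

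The NMR wording adds a contradiction. If NMR turns out not to be significant, an analyst who follows section 12 leaves it out and thereby departs from section 11.D. A reader cannot tell from the protocol whether NMR is in the primary model. At stake are prespecification and consistency, and possibly the estimates for 1A and 1B. The check below asks how much those estimates could move.

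**Working it through.** **1. The two sections side by side.** NMR is unconditional in section 11.D b and conditional in section 12. Both can be followed if NMR is significant; they cannot if it is not. The hormones are confined to women in both places and are not on the list governed by the significance rule. What differs there is only that they will be used in one place and considered in the other.

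**2. How often the screen changes the model.** Assumptions: screening level 0.05 (section 12 states 0.05 only for the main hypotheses), six independent terms, no true effects.
- At least one term kept: 1 − 0.95^6 = 0.265, or 26%.
- Two outcomes screened separately and uncorrelated: each term differs with probability 2 × 0.05 × 0.95 = 0.095, so the models differ with probability 1 − 0.905^6 = 0.45.
- With outcome correlation 0.5, 0.7 or 0.9 (400,000 draws; two 2-df and four 1-df tests), the models differ in 40%, 34% or 22% of trials.

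**3. Which terms can reach the hypothesis tests.** For one subject, write m, c for menthol and control flavor, and n, s for nicotine and saline. Let b be the subject-level effect, δ the session-day effect and π the infusion-order effect.
- Interaction contrast: (Y_mn − Y_ms) − (Y_cn − Y_cs). The b terms cancel. The δ terms also cancel, because nicotine and saline are given in the same session. The π terms need not cancel, because infusion order is random in each session (section 11.A).
- Across-session comparison: Y_mn − Y_cn. Here δ for the menthol day minus δ for the control day remains, and so does a difference in π.

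Mixed-model fits to simulated data agree on the first point. With complete data, the four 1B coefficients were −0.3481, 0.1929, −0.2566 and 0.1316 both with and without a race main effect (Wald 1.197 both times). With whole sessions missing, they were unchanged to four decimals (Wald 1.608 and 1.606). The same algebra holds for sex, NMR and FTND as main effects.

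**4. Size for infusion order.** Simulation: 60 subjects × 3 sessions × 3 infusions, random infusion order, residual SD 1, drift per infusion assumed, 4-df tests of 1A and 1B.

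| Result | Drift 0.1 SD | Drift 0.2 SD |
|---|---|---|
| Order term kept by the screen | 36.8% | 92.0% |
| Mean shift of estimates | 0.09 SE | 0.16 SE |
| Verdict differs with vs without the term, no true effect (1A / 1B) | 1.3% / 1.3% | 2.1% / 1.5% |
| Same, at about 50% power (1A / 1B) | 4.5% / 4.4% | 7.9% / 6.1% |

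**5. Size for session day.** For menthol plus nicotine against control flavor plus nicotine, a drift of 0.1 to 0.2 SD per day moves the estimate by about 0.1 to 0.16 SE. The verdict under the screen differs from that with the term always included in about 1% of trials with no true effect and 3–4% at about 50% power.

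**6. Type I error under the screen.** At infusion drifts of 0, 0.1, 0.2 and 0.5 SD it is 5.1, 4.9, 5.0 and 5.4% for 1A, and 5.0, 5.0, 4.7 and 4.2% for 1B (3,000 replicates; simulation SE √(0.05 × 0.95/3,000) = 0.4 points). A separate run for 1A with infusion-order and session-day drift together, at steps of 0, 0.15, 0.3 and 0.6 SD, gave 4.1, 5.3, 4.3 and 3.9% (1,500 replicates; SE 0.6 points). With the order terms always kept, it gave 4.4, 5.3, 4.3 and 3.9%. All are within about two simulation SEs of 5%.

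**7. Cost of always keeping the order terms.** Each three-level term uses 2 df. Always keeping infusion order raises the SE by 0.3%.

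**The case against.** The best defence is that nothing important follows from the rule. The tested factors and interactions are fixed, both orders are randomised, and type I error is not inflated. Most of the model differences counted in step 2 involve terms that cannot move the interactions, and those percentages rest on a screening level and per-outcome screening that the protocol does not state. All of this stands, and it is why the point is minor. A separate analysis plan could supply the level. It would not undo the fact that the protocol itself states a data-dependent rule and contradicts it for NMR.

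On NMR, the statement in section 11.D does not name the primary model, and the clash arises only if NMR is not significant. That is fair, but the protocol gives no way to know in advance which case will apply.

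Two stronger readings are tempting. A reader might infer that the hormones are also in conflict over the primary model. The documents do not support this, since both passages confine them to women.

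A reader might also infer that 1B is wrongly analysed. The background section ties menthol preference to race among young smokers (71.9% in African-Americans against 41% in non-Hispanic Caucasians), and race as a plain covariate cannot adjust the three-way interaction. The algebra is right, but 1B is worded as a difference between preference groups, and a difference that partly reflects racial make-up is still that difference. The protocol does not establish that race modifies the menthol × nicotine effect. Section 11.B offers only a "preliminary evaluation of potential sex and/or race differences in sensory and hedonic responses to menthol", using the dose-finding data, in which no nicotine was given. A supportive race × nicotine × menthol analysis is an option, and its absence is not an error.

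**Conclusion.** The point holds as a minor fault of prespecification and consistency. The adjustment terms of the main-outcome model depend on the data and may differ between the two main items, and sections 11.D and 12 conflict on NMR whenever it is not significant. The hormone wording is a softer mismatch, limited to the analysis of women.

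The effect on the conclusions is small. No inflation of type I error was found, and the verdict changed in about 1–2% of trials with no true effect and 3–8% at about 50% power. These figures assume a 0.05 screen, linear drift of 0.1 to 0.2 residual SD per step, 60 subjects with all sessions, and covariates entered as main effects. The protocol gives no drift estimate, so the range is illustrative. The contradiction on NMR needs none of these assumptions.

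**What to change.** In section 12, replace the significance rule with a fixed specification. Infusion order and session day are always in the model, together with a covariate list that is settled in advance, kept whatever its p-values and identical for good effects and drug liking. State in both section 11.D b and section 12 whether baseline NMR is on that list. Use the same wording in both places for estradiol and progesterone in the secondary analysis of women.

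The cost is a change of wording, a few degrees of freedom and under about 1% in standard error. No new data are needed, and the tests of 1A and 1B keep their form.
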